## 2.4 Protocol Amendments

Table 2.4-1 summarizes changes in the protocol that affect the analyses.

**Table 2.4-1: Summary of Changes to the Protocol**

Description of Change	Brief Rationale
Amendment 1:	
Phase 2 primary endpoint from ORR to PFS.	
Updated interim PFS analysis (PFS IA) to include all participants from Phase 2 and clarified results of the interim analysis.	PFS is the better predictor of final trial success Better use of the information collected to make a decision.
Revised some endpoint language for better clarity	Revised for clarity. Better timing for procedure.
Updated tumor assessments from Week 49 to 52.	
Amendment 2:	
Added PFS2 as an exploratory objective.	
Amendment 3:	
Synopsis Table 4-1 Objectives and Endpoints	Revised “Median duration of response (DOR)” to “DOR” to remove Median DOR as an endpoint. Added a separate analysis of GP5 in the FACT-M.
Synopsis Figure 5.1-1 Study Diagram 10.2.2. Efficacy Analyses 10.2.5 Interim Analyses	Revised text related to the interim and final analyses The study recently proceeded to phase 3 at the interim PFS analysis indicating that it met or exceeded a PFS HR threshold of 0.8. Assuming a statistically significant PFS result at PFS FA, added that there will be interim analyses of OS. The first interim analysis of OS (OS IA1) will be performed at the time of a statistically significant PFS result. If OS IA1 is not statistically significant, the second interim analysis of OS (OS IA2) will be performed when a minimum of 90% (270/300) of the expected deaths have occurred. If OS IA2 is not statistically significant, the final OS analysis will be performed when at least 300 deaths have occurred.
7.3 Blinding	Specified that the analysis team reporting to the Data Monitoring Committee (DMC) is external to BMS

**Table 2.4-1: Summary of Changes to the Protocol**

Description of Change	Brief Rationale
10.1 Sample Size Determination	Added text on non-proportional hazards for sample size justification for progression free survival (PFS) estimation
10.2.2. Efficacy Analyses	
Revised the Phase 3 secondary endpoints hierarchy (1. Overall survival [OS] 2. Overall response rate [ORR]). In the event of a statistically significant PFS result, evaluating OS more formally would be considered more clinically meaningful than ORR. OS is considered a more relevant endpoint for evaluation of clinical benefit in the melanoma landscape compared to ORR. In study CA209-067 in previously untreated metastatic melanoma, overall survival at 5 years was remarkable at 52% in the nivolumab-plus-ipilimumab group and 44% in the nivolumab group, as compared with 26% in the ipilimumab group.1 In addition, in the event of a statistically significant PFS result, evaluating OS more formally would be considered more clinically meaningful than ORR.2 Therefore OS will be tested hierarchically at the time of statistically significant PFS followed by ORR (if OS is statistically significant and at the time that ORR data are mature).Therefore OS will be tested hierarchically at the time of positive PFS (if DMC states PFS is statistically significant) followed by ORR (if OS is positive and when ORR reaches maturity).
 
Provided more detail on the Phase 2 Primary statistical methods
 
Divided the “Testing Strategy” into separate sections for Phase 2 and Phase 3
 
Updated the Phase 3 Testing Strategy text to include the plan and conditions for analysis of OS
 
Updated the Phase 2 Testing Strategy text to include when the sponsor would be unblinded in the case of a Phase 2 study

## 2.5 Data Monitoring Committee

A DMC will be established to provide oversight of safety and efficacy considerations and to provide advice to the Sponsor regarding actions the committee deems necessary for the continued protection of participants enrolled in this study. The DMC will be charged with assessing such actions in light of an acceptable benefit/risk profile for relatlimab and nivolumab. The DMC will act in an advisory capacity to BMS and will monitor participant safety and evaluate the available efficacy data for the study. The oncology therapeutic area of BMS has primary responsibility for design and conduct of the study.

The DMC will convene to assess the results of the interim analyses and provide its recommendations. Additional details concerning DMC oversight are provided in the DMC charter.

In addition, a BICR will be utilized in this study for determination of BICR-assessed endpoints. The BICR will review all available tumor assessment scans for all treated participants. Details of BICR responsibilities and procedures are specified in the BICR charter.

### 3 OBJECTIVES

Table 3-1 summarizes the study objectives and endpoints. Section 4 goes into more detail about the endpoint definitions.

**Table 3-1: Study Objectives and Endpoints**

Objectives	Endpoints
Phase 3 Primary Objective	
The Phase 3 primary objective is to compare PFS of BMS-986213 to nivolumab monotherapy in participants with previously untreated, unresectable, or metastatic melanoma.	PFS time as assessed by a Blinded Independent Central Review (BICR), using RECIST v1.1. PFS is defined as the time between the date of randomization and the first date of documented progression, or death due to any cause, whichever occurs first.
Phase 3 Secondary Objectives	
To compare OS of BMS-986213 to nivolumab monotherapy in participants with previously untreated, unresectable or metastatic melanoma.	OS is defined as the time between the date of randomization and the date of death due to any cause.
To compare ORR of BMS-986213 to nivolumab monotherapy in participants with unresectable or metastatic melanoma	ORR as assessed by a BICR. The ORR is defined as the number of subjects with a best overall response (BOR) of complete response (CR) or partial response (PR) divided by the number of randomized subjects for each treatment group. The BOR is defined as the best response designation, recorded between the date of randomization and the date of objectively documented progression per RECIST v1.1 or the date of subsequent anti-cancer therapy, whichever occurs first.
Phase 3 Tertiary/Exploratory Objective	
To evaluate duration of and time to objective response	Duration of response (DOR) is defined as the time between the date of first response to the date of first documented tumor progression (per RECIST v1.1) or death due to any cause. Time to objective response (TTR) is defined as the time from randomization to the date of the first documented CR or PR.
To evaluate PFS, ORR, DOR, and OS of BMS-986213 to nivolumab monotherapy in subgroups based on combinations of LAG-3 expression ( $\geq 1\%$ expression versus $< 1\%$ expression) and PDL-1 status ( $\geq 1\%$ tumor cell surface expression versus $< 1\%$ tumor cell surface expression) among participants with unresectable or metastatic melanoma treated with BMS-986213 compared to those treated with nivolumab monotherapy.	PFS time as assessed by a BICR using RECIST v1.1. ORR as assessed by a BICR. DOR. TTR. OS.
To evaluate the difference in symptom burden between participants with unresectable or metastatic melanoma treated with BMS-986213 and those treated with nivolumab monotherapy.	Time to meaningful symptomatic deterioration (TTSD) as measured by the Functional Assessment of Cancer Therapy – Melanoma (FACT-M) Melanoma Subscale (MS).

**Table 3-1: Study Objectives and Endpoints**

Objectives	Endpoints
To characterize the pharmacokinetics (PK) of relatlimab and nivolumab in subjects with unresectable or metastatic melanoma treated with BMS-986213 and those treated with nivolumab monotherapy.	PK parameters, influence of intrinsic and extrinsic covariates will be characterized using population PK models.
To characterize immunogenicity of relatlimab and nivolumab in subjects with unresectable or metastatic melanoma treated with BMS-986213 and those treated with nivolumab monotherapy.	Incidence of anti-drug-antibody (ADA) to relatlimab and nivolumab when administered in combination with nivolumab.
To explore potential exposure-response relationships in subjects treated with BMS- 986213.	Potential exposure response relationship (PD effect, efficacy, and select safety) will be evaluated using integrated analysis.
To explore potential biomarkers associated with clinical efficacy (ORR, PFS, and OS) by analyzing biomarker measures within the tumor microenvironment and periphery (e.g., tumor, serum and PBMCs) as related to clinical outcomes.	Association measures of select biomarkers and key efficacy endpoints (e.g., ORR, PFS, and OS)
To characterize changes in cancer-related symptoms and quality of life for participants with unresectable or metastatic melanoma treated with BMS-986213 and those treated with nivolumab monotherapy	Summary measures of FACT-M total and subscale scores (and changes) following treatment.
To characterize participant perceptions of the bothersomeness of symptomatic AEs, based on FACIT GP5 item as found in the FACT-M.	
 
Summary changes and frequency of responses in FACIT GP5 item measuring bother due to side effects of treatment.
 

To characterize changes in overall health status and health utility for participants with unresectable or metastatic melanoma treated with BMS-986213 and those treated with nivolumab monotherapy.	Summary measures of EQ-5D-3L visual analog scale (VAS) and utility index scores.
To characterize changes in work productivity and activity impairment for participants with unresectable or metastatic melanoma treated with BMS-986213 and those treated with nivolumab monotherapy	Summary measures of Work Productivity and Activity Impairment: General Health (WPAI:GH) work productivity loss, activity impairment, presentism, and absenteeism scores.
To evaluate PFS, PFS 2, ORR, and DOR of BMS-986213 to nivolumab monotherapy in participants with previously untreated, unresectable, or metastatic melanoma	
PFS and PFS 2 time as assessed by investigator using RECIST v1.1.
 
ORR as assessed by investigator.
 
DOR.

To evaluate treatment-free interval (TFI) defined as time from last dose of study treatment to the start of subsequent systemic therapy or the last known date alive (for those who never received subsequent cancer therapy)	TFI
Phase 3 Safety Objective:	
To assess the overall safety and tolerability of BMS-986213 and of nivolumab monotherapy.	Rate of AEs, SAEs, AEs leading to discontinuation of treatment, deaths, and laboratory abnormalities.

**Table 3-1: Study Objectives and Endpoints**

Objectives	Endpoints
Phase 2 Primary Objective:	
The Phase 2 primary objective is to compare PFS of BMS-986213 to nivolumab monotherapy in participants with previously untreated, unresectable, or metastatic melanoma.	PFS time as assessed by BICR, using RECIST v1.1. PFS time is defined as the time between the date of randomization and the first date of documented progression, or death due to any cause, whichever occurs first.
Phase 2 Secondary Objectives:	
To estimate the treatment effect, measured by ORR, as determined by BICR using RECIST v1.1 in all-comers and in subgroups based on combinations of LAG-3 expression ( $\geq 1\%$ expression versus $< 1\%$ expression) and PDL-1 status ( $\geq 1\%$ tumor cell surface expression versus $< 1\%$ tumor cell surface expression) among participants with unresectable or metastatic melanoma treated with BMS-986213 compared to those treated with nivolumab monotherapy.	ORR as assessed by BICR.
To evaluate DOR and PFS rates at pre-specified time points (e.g., 24 weeks) based on BICR assessments using RECIST v1.1 in the randomized population (for DOR) and in subgroups based on combinations of LAG-3 expression ( $\geq 1\%$ expression versus $< 1\%$ expression) and PDL-1 status ( $\geq 1\%$ tumor cell surface expression versus $< 1\%$ tumor cell surface expression) among subjects with unresectable or metastatic melanoma treated with BMS-986213 compared to those treated with nivolumab monotherapy.	DOR. PFS time as assessed by BICR using RECIST v1.1.
To assess the 1- and 2-year OS rate in the randomized population and in subgroups based on combinations of LAG-3 expression ( $\geq 1\%$ expression versus $< 1\%$ expression) and PDL-1 status ( $\geq 1\%$ tumor cell surface expression versus $< 1\%$ tumor cell surface expression) among subjects with unresectable or metastatic melanoma treated with BMS-986213 and those treated with nivolumab monotherapy.	OS is defined as the time between the date of randomization and the date of death due to any cause.
Phase 2 Exploratory Objectives:	
To characterize the PK of relatlimab and nivolumab in subjects with unresectable or metastatic melanoma treated with BMS-986213 and those treated with nivolumab monotherapy.	Summary measures of PK parameters based on population PK models including influence of intrinsic and extrinsic covariates
To characterize the immunogenicity of relatlimab and nivolumab in subjects with unresectable or metastatic melanoma treated with BMS-986213 and those treated with nivolumab monotherapy.	Incidence of ADA to relatlimab and ADA of nivolumab when administered in combination with relatlimab

**Table 3-1: Study Objectives and Endpoints**

Objectives	Endpoints
To assess the PD effects of BMS-986213 based on select biomarkers in the peripheral blood and tumor biopsyspecimens.	Summary measures of change (or % change) from baseline in various biomarkers.
To characterize T-cell function during treatment of BMS-986213.	Summary of pre- treatment levels and of changes in T cells levels observed on- treatment.
To explore potential exposure-response relationships (e.g., with efficacy, receptor occupancy, pharmacodynamic effects) in subjects treated with BMS-986213.	Measures of Potential PK exposure response relationship (with pharmacodynamic effects, efficacy and select safety)
To evaluate ORR, DOR, and PFS and PFS2 rates at pre-specified time points (e.g., 24 weeks) based on investigator assessments using RECIST in the randomized population and in subgroups based on combinations of LAG-3 expression ( $\geq 1\%$ expression versus $< 1\%$ expression) and PDL-1 status ( $\geq 1\%$ tumor cell surface expression versus $< 1\%$ tumor cell surface expression) among subjects with unresectable or metastatic melanoma treated with BMS- 986213 and those treated with nivolumab monotherapy.	ORR. DOR. TTR. PFS and PFS2 time using RECIST v1.1.
Phase 2 Safety Objective:	
To assess safety and tolerability among participants with unresectable or metastatic melanoma treated with BMS-986213 compared to those treated with nivolumab monotherapy.	Rate of AEs, SAEs, AEs leading to discontinuation of treatment, deaths, and laboratory abnormalities.

## **4 ENDPOINTS**

### **4.1 Efficacy**

#### **4.1.1 Progression-Free Survival**

Two definitions are used for analysis of Progression-Free Survival (PFS). The primary definition accounts for subsequent therapy by censoring at the last evaluable tumor assessment on or prior to the date of subsequent therapy. The secondary definition is irrespective of subsequent therapy and does not account for subsequent therapy.

Clinical deterioration in the absence of unequivocal evidence of progression (per RECIST v1.1 criteria) is not considered progression for purposes of determining PFS.

PFS rate at time  $T$  is defined as the probability that a subject has not progressed and is alive at time  $T$  following randomization. PFS rates at fixed time points (e.g., 6 months, depending on the minimum follow-up) are defined as the probability that a subject has not progressed and is alive at time  $T$  following randomization.

The first on-study tumor assessment is scheduled to be conducted at 12 weeks ( $\pm 1$  week) following randomization. Subsequent tumor assessments are scheduled every 8 weeks ( $\pm 1$  week) up to 52, then every 12 weeks ( $\pm 1$  week) until disease progression.

##### **4.1.1.1 Primary Definition of Progression-Free Survival (Accounting for Subsequent Therapy)**

[figure not shown]
The primary definition of PFS (PFS truncated at subsequent therapy) is defined as the time between the date of randomization and the date of first documented tumor progression, based on BICR assessments (per RECIST v1.1 criteria), or death due to any cause, whichever occurs first.

Subjects who die without a reported progression will be considered to have progressed on the date of their death. The following censoring rules will be applied for the primary definition of PFS:

- Subjects who did not progress or die will be censored on the date of their last evaluable tumor assessment.
- Subjects who did not have any on study tumor assessments and did not die will be censored on their date of randomization.
- Subjects who receive subsequent anti-cancer therapy prior to documented progression will be censored at the date of the last evaluable tumor assessment conducted on or prior to the date of initiation of the subsequent anti-cancer therapy.
- Subjects who did not have a documented progression and received subsequent anti-cancer therapy will be censored at the date of the last evaluable tumor assessment conducted on or prior to the initiation of the subsequent anti-cancer therapy.

Censoring rules for the primary definition of PFS (PFS truncated at subsequent therapy) are presented as follows in [Figure 4.1.1.1-1](#) and in [Table 4.1.1.1-1](#).

**Figure 4.1.1.1-1: PFS Primary Definition**

**Table 4.1.1.1-1: Censoring Scheme used in Primary Definition of PFS**

Situation	Date of Progression or Censoring	Outcome
No baseline tumor assessments*	Date of randomization	Censored
No on study tumor assessments and no death*	Date of randomization	Censored
Subsequent anti-cancer therapy started without death or progression per RECIST v1.1 reported prior or on the same day	Date of last evaluable tumor assessment prior to or on the date of initiation of the subsequent anti-cancer therapy	Censored
Documented progression per RECIST v1.1 and no new anti-cancer started before	Date of the first documented progression per RECIST v1.1 (excludes clinical progression)	Progressed
No progression and no death, and no new anti-cancer therapy started	Date of last evaluable tumor assessment	Censored
Death without progression per RECIST v1.1 and no new anti-cancer started before	Date of death	Progressed

\* Tumor assessments and death if any, occurring after start of subsequent anti-cancer therapy are not considered. Note: subjects with measurable disease per Investigator but no measurable disease per BICR will be included in the analysis.

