5.1.1 Data Monitoring Committee and Other External Committees

When required, adjudicated events will be submitted to the DMC and Health Authorities for review on a specified timeframe in accordance with the adjudication documentation.

A DMC will be established to provide oversight of safety and efficacy considerations and to provide advice to the Sponsor regarding actions the committee deems necessary for the continued protection of participants enrolled in the study. The DMC will be charged with assessing such actions in light of an acceptable benefit/risk profile for relatlimab and nivolumab. The DMC will act in an advisory capacity to BMS and will monitor participant safety and evaluate the available efficacy data for the study. The oncology therapeutic area of BMS has primary responsibility for design and conduct of the study.

The DMC will convene to assess the results of the interim analyses (see [Section 10.2.5](#) and provide its recommendations. Additional details concerning DMC oversight are provided in the DMC charter.

In addition, a BICR will be utilized in this study for determination of BICR-assessed endpoints. The BICR will review all available tumor assessment scans for all treated participants. Details of BICR responsibilities and procedures will be specified in the BICR charter.

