**Figure 4.1.1.2-1: PFS Secondary Definition**

**Table 4.1.1.2-1: Censoring Scheme for Secondary definition of PFS**

Situation	Date of Progression of Censoring	Outcome
No baseline tumor assessment	Date of randomization	Censored
No on-study tumor assessments and no death	Date of randomization	Censored
Documented progression per RECIST v1.1	Date of first documented progression per RECIST v1.1 criteria (excludes clinical progression)	Progressed
No progression and no death	Date of last evaluable tumor assessment	Censored
Death without progression per RECIST v1.1	Date of death	Progressed

Note: subjects with measurable disease per Investigator but no measurable disease per BICR will be included in the analysis.

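### Both SAP PFS censoring tables censor participants without a baseline tumor assessment at randomization with no exception for death, which conflicts with the tables' own death row

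*SAP*

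**What the plan says.** SAP 4.1.1.1 defines primary PFS from randomization to progression by blinded independent central review (BICR) "or death due to any cause, whichever occurs first". The text adds: "Subjects who die without a reported progression will be considered to have progressed on the date of their death". Its bullets censor at randomization only participants who had no on-study assessment and did not die. They contain no rule for a missing baseline. Protocol 10.2.2 has the same death rule and the same limited censoring rule, and also says nothing about a missing baseline.

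Table 4.1.1.1-1 adds a row that the text does not have:

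- Row 1, "No baseline tumor assessments": censored at randomization.
- Row 2, "No on study tumor assessments and no death": censored at randomization.
- Last row, "Death without progression per RECIST v1.1 and no new anti-cancer started before": event on the date of death.

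Rows 1 and 2 share a footnote: "Tumor assessments and death if any, occurring after start of subsequent anti-cancer therapy are not considered".

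Table 4.1.1.2-1, for the secondary (ITT) definition, has the same unconditional baseline row without the footnote. It is followed by "No on-study tumor assessments and no death" and, at the end, a death row. SAP 7.5.1 lists reasons for PFS censoring. Missing baseline is one category with no death condition, and the category after it does carry one.

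**The concern.** Row 2 shows that the authors knew a death should override censoring at randomization. Row 1 does not say so. A programmer who reads the table from the top would set a participant with no baseline scan to censored at day 0 even if that participant died. A programmer who starts from the text, or from the death row, would record an event. Both would be following the SAP.

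The primary analysis is in all randomized participants, and death from any cause is part of the endpoint. Censoring a known death at day 0 would be wrong under that definition: the same death would count for OS and vanish from PFS, along with the participant's time at risk. The ITT definition is the natural check on the primary censoring rules, but it carries the same gap.

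**Working it through.** **Case to classify.** A randomized participant has no baseline tumor assessment, starts no subsequent anti-cancer therapy and dies with no progression recorded.

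- SAP 4.1.1.1 definition: event.
- SAP 4.1.1.1 death rule: event on the date of death.
- SAP 4.1.1.1 bullet on censoring at randomization: does not apply, because the participant died.
- Protocol 10.2.2: event on the date of death.
- Table 4.1.1.1-1, row 1: censored at randomization.
- Table 4.1.1.1-1, row 2: does not apply, because the participant died.
- Table 4.1.1.1-1, last row: event on the date of death. It does not ask for a baseline scan.
- Table 4.1.1.2-1: first row censored, last row event.

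The table gives two opposite outcomes for one participant, and the SAP states no precedence.

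**Do the notes resolve it?** The footnote only sets aside assessments and deaths after subsequent therapy; this participant had none. The other note under the tables keeps in the analysis participants whose disease is measurable per investigator but not per BICR. That concerns measurability, not an absent baseline. Neither note settles the case.

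**Does SAP 7.5.1 resolve it?** No. That list describes participants already classed as censored, so it does not define the rule. It does repeat the category without the death condition, so it gives a programmer no reason to doubt row 1.

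**Size.** The documents do not report how many participants lacked a baseline assessment, or how many of them died.

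The plan's own figure comes first. Inputs from SAP 5 and 5.2 are 365 events, HR 0.73 and 1:1 allocation, with two-sided alpha 0.05 overall and 0.049 at the final PFS analysis. By Schoenfeld's formula, power = Φ(½·√D·|ln HR| − z), where z is the two-sided critical value:

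- ½ × √365 × |ln 0.73| = 9.552 × 0.3147 = 3.006.
- Alpha 0.05: Φ(3.006 − 1.960) = 85.2%.
- Alpha 0.049: Φ(3.006 − 1.969) = 85.0%.

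This reproduces the stated power of about 85%.

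Now assume that k deaths are lost and not replaced (k is an assumption), with alpha 0.049:

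- k = 2 (2/365 = 0.5% of events): 84.8%.
- k = 4 (1.1%): 84.6%.
- k = 7 (1.9%): 84.3%.
- k = 14 (3.8%): 83.6%.

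For k = 14, 2% of the 700 participants (14/700) would have to lack a baseline assessment and also die. Zero is equally compatible with the documents. The final analysis is triggered at 365 or more counted events, so an uncounted death would normally be replaced by a later event. The real consequence is which deaths count, not planned power.

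**The case against.** The strongest reply is that this is a dropped clause, not an analysis decision. The definition, the text and the protocol all count the death, and the table's own death row agrees with them. The footnote on row 1 mentions death after subsequent therapy, which would serve little purpose if row 1 already ignored every death. This stands: the intended meaning is fairly clear. It does not remove the conflict in the table, which is the part most likely to be programmed.

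Row 1 should also be nearly empty. Protocol 6.1 requires measurable disease by CT or MRI, Protocol 9.1 requires baseline imaging within 28 days before randomization, and Protocol 9 requires screening to be complete before randomization and allows no waivers. Any case would be visible too: SAP 7.5.1 tabulates censoring reasons by arm, and SAP 7.5.2 provides a by-subject listing of censoring reasons under both definitions. These points stand and limit the effect.

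A reader might infer that never-treated participants fall into row 1 as a group, because Protocol 5.1.1 says "The BICR will review all available tumor assessment scans for all treated participants". The documents do not support this. That sentence does not say that only treated participants are read. Protocol 9.1.2.1 asks sites to send all scans to the core lab. Row 1 does not say that the missing baseline is the central one. SAP 7.5.1 lists never-treated participants separately, under off-study.

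A reader might also infer that no planned PFS analysis would count these deaths. That goes too far. Investigator-assessed PFS is planned (SAP 7.5.1 and 7.5.2) and would count the death of a participant who lacked only a central baseline. If there were no baseline scan at all, and the same censoring scheme were used, that analysis would meet the same conflict.

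**Conclusion.** The inconsistency is real and can be checked on the page: one row lacks a condition in both PFS tables and in the SAP 7.5.1 category, and the outcome it gives contradicts the death row, the SAP text and Protocol 10.2.2. It would be too strong to say that the plan removes these deaths from PFS. The table contradicts itself, and most of the plan counts them.

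The expected effect on the primary result is very small. That judgement rests on the entry requirements for imaging and measurable disease, since no counts are given; the power figures above depend on assumed numbers of deaths. No direction of bias can be stated without counts by arm. The point is still worth correcting, because it concerns the derivation of the primary endpoint and costs almost nothing to settle.

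**What to change.** In Table 4.1.1.2-1, limit the missing-baseline row to participants who did not die. In Table 4.1.1.1-1, limit it to those with no death before subsequent anti-cancer therapy. Add the no-death condition to the missing-baseline category in SAP 7.5.1. Deaths in participants without a baseline assessment then follow the existing death row, and the tables match the text and the protocol.

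SAP 5.2.1 records that primary PFS was tested on 09MAR2021, was significant and led to subject-level unblinding. The edit should therefore be entered as a dated clarification, not as a new rule. The sponsor should state which row the analysis program applied and how many deaths per arm were affected. If none were, the matter is closed. If any were censored, PFS should be reported with them as events, under both definitions, beside the result already obtained.

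The cost is one clause in three places, a check of the existing by-subject listing and, if needed, one rerun. No new data are required.
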